10.0 Assessment of Safety

- 10.1 Best Corrected Visual Acuity
- 10.2 Examination of Corneal Epithelium With Slit Lamp Biomicroscopy
- 10.3 Intraocular Pressure
- 10.4 Cataract Assessment
- 10.5 Vital Signs
- 10.6 Adverse Events
 - 10.6.1 Definition of Adverse Events
 - 10.6.2 Relationship to Study Drug
 - 10.6.3 Adverse Event Intensity Grading
 - 10.6.4 Likely Adverse Events
 - 10.6.5 Serious Adverse Events
 - 10.6.6 Serious Adverse Events Reporting
- 11.0 Statistical Considerations
- 12.0 Direct Access to Source Documents
- 13.0 Quality Control and Assurance
- 14.0 Ethics
- 15.0 Subject Informed Consent
- 16.0 Institutional Review
- 17.0 General Information
- 18.0 Data Handling and Record Keeping
 - 18.1 Confidentiality
 - 18.2 Case Report Forms
 - 18.3 Record Keeping
 - 18.4 Financial
 - 18.5 Publication

References

Abbreviations

AV	Adenovirus
AE	Adverse event
API	Active Pharmaceutical Ingredient
BCVA	Best corrected visual acuity
BP	Blood Pressure
CBC	Complete Blood cell Count
CRF	Case Report Form
CRO	Contract Research Organization
DR	[name] MD (Co-investigator)
ECG	Electrocardiogram
ECC	Corneal Endothelial Cell Count
ETDRS	Early Treatment Diabetic Retinopathy Study
EW	[name] (Principal investigator)
FDA	Food and Drug Administration
GCP	Good Clinical Practices
HIPAA	Health Insurance Portability and Accountability Act
ICH	International Conference on Harmonization
IND	Investigational New Drug
ITT	Intent-to-treat
PCR	Polymerase Chain Reaction
IRB	Institutional Review Board
QID	Four times daily
SAE	Serious Adverse Event
SCH-1	The investigation drug
SD	Standard Deviation
SPK	Superficial Punctate Keratitis
TOC	Test of Cure

Synopsis

Title	SCH1 In The treatment of Acute Infectious Conjunctivitis
Investigator	[name] MD [name]
Sponsor	[name] MD MEETH Ophthalmology [name]
Indication	Treatment of acute infectious conjunctivitis, bacterial and/or viral.
Objective	The objective of this study is to evaluate the efficacy of Sasch1 in the treatment of acute infectious conjunctivitis.
Eligibility Criteria	
Inclusion Criteria
 
 • Conjunctivitis (as defined below) within 72 hours of initial ocular symptoms. • At least 18 years of age. • Subjects capable of understanding the purpose and risks of the study, and able to give informed consent. • Conjunctivitis diagnosis defined as presence of the two cardinal signs of acute conjunctivitis- 1) bulbar conjunctival injection and 2) conjunctival discharge/exudates. • A three-point rating scale (0=absent, 1=mild, 2=moderate, 3=severe) will be employed to grade conjunctival discharge/exudates. • All patients will require a rating of 1(mild) or greater for conjunctival discharge/exudates. • Patients will require a rating of 1 (mild) for bulbar conjunctival injection.
	
Exclusion Criteria
 
 • Conjunctivitis greater than 72 hours after initial ocular symptoms • Corneal ulcer, endophthalmitis, or any other confounding infection of the eye • Patients taking topical anti-inflammatory medications on a chronic basis • Known steroid glaucoma responders • Active herpes ocular infection • Pregnant women • Known allergy to chlorhexidine
Trial Design	This is a phase II single-center, prospective, placebo-controlled, randomized study of SCH1 in the treatment of acute infectious conjunctivitis. Study drug will be evaluated against vehicle.
Primary Endpoint	Clinical cure defined as rating of 0/3 for bulbar conjunctival injection and 0/3 for conjunctival exudates/discharge or clinical success defined as an overall decrease by 3 in the sum of both grades.

Secondary	
 Patients will keep a self log of symptom score each of the 5 days of the study
Number of Subjects	
 30 (15 per treatment arm)
Target Population	
 Patients with infectious conjunctivitis defined by bulbar conjunctival injection (rated at least 1 on 3 point grading scale) and conjunctival exudates / discharge (rated at least 1 on 3 point grading scale). Patients greater than one year of age. Patients of any race or ethnic group.
Length of Study	
Enrollment period: 12 months Treatment period: 5 days Overall duration: 6 months 5 days

Study Drug	
Subjects will be randomized to one of the following treatment arms: Treatment Arm A: SCH1 Treatment Arm B: Placebo (Vehicle only)

Assessment of Safety	
 Incidence of SPK at day 1 Incidence of SPK at Day 5 Intraocular pressure at Day 5 
VA loss of 4 or greater lines on Snellen VA Chart

Interim Analysis and Safety Monitoring	
 Safety data will be reviewed by [name], Medical Monitor and Sponsor. A summary report of the safety points will be created every 3 months, as well as the end of the study, and reported to the IRB.
Statistical Analysis	
The statistical analysis will evaluate: 1) The overall clinical success rate defined as the percentage of study participants achieving a clinical cure by Day 5 or an overall decrease in the sum of both grades by 3; 2) Microbiological cure rate defined as the percentage of study participants who demonstrate elimination of pre-treatment pathogen(s) by the Day 5 TOC exam.
 
A statistical difference in clinical cure rate will be defined where the 95% confidence limit for the difference in the two study groups (SCH1 vs. Placebo) is greater than (+/-)15%.
 
All data will be examined employing an “Intent to Treat” analysis for all patients. Mean outcome variables in the two study groups will be compared. Statistical means between both study groups will be analyzed by both parametric and non-parametric tests to allow for deviations of data from normal distributions.

Schedule of Visits and Assessments

	Screen / Visit 1	Visit 2	Visit 3
	Day 1	Day 3	Day 5
General Exams			
Informed consent	x		
Inclusion/exclusion criteria	x		
Medical history	x		
Vital signs	x		x
Physical Exam	x		
Patient comfort exam	x	x	x
AE assessment	x	x	x
Current meds	x	x	x
Ophthalmic exams			
BCVA	x		x
Visual acuity	x	x	x
Anterior segment slit lamp exam and tonometry	x	x	x
Dilated fundus exam	x		x

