2.0 BACKGROUND

2.1 Acute Infectious Conjunctivitis

Acute infectious conjunctivitis (“pink eye”) is one of the most common and most contagious ocular infections in the US and the rest of the world. It is usually caused by either bacteria (both Gram-positive and Gram-negative) or more commonly, multiple serotypes of human adenovirus. In addition to the direct damage caused by the infection itself, the body’s stereotyped immune response often overwhelms the delicate structures of the eye and leads to secondary, often permanent, inflammatory damage. While some combination antibiotic/anti-inflammatory drugs have been useful for routine bacterial conjunctivitis, all are suffering from increasing antibiotic resistance, and are contraindicated in the case of suspected viral infection due to their propensity to worsen the duration and severity of viral infections.

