2.4 Study Rationale

Acute infectious conjunctivitis is a leading cause of ocular morbidity, epidemic eye infection, lost productivity, patient discomfort and in some cases permanent visual compromise. The infectious agent is frequently viral in origin and frequently bacterial in origin with very little to reliably distinguish one from the other. Concomitant inflammatory damage often occurs and can lead to long term ocular morbidity. No current treatments are capable of treating both viruses and bacteria. Additionally no current combination antibiotic/steroid combinations can safely be administered in suspected viral infections. The objective of this study is to assess the efficacy of SCH1

as a first-line treatment for ocular inflammation and infection in the setting of an acute viral or bacterial conjunctivitis infection.

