4.0 Endpoints

4.1 Primary Endpoints

The primary endpoint will be the achievement of a clinical cure defined as a rating of 0/3 for bulbar conjunctival injection and 0/3 for conjunctival exudates/discharge or clinical success defined as an overall decrease by 3 in the sum of both scores.

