Descriptive statistics (i.e. mean and standard deviations [SD] for normally distributed data, median with interquartile ranges [IQR] for non-normally distributed data) were calculated for all relevant measures. Percentage breakdowns will be used for categorical variables (ie: gender, age). All P-Values will be two-sided with statistical significance evaluated at the 0.05 alpha level.

All analyses were performed in SAS Version 9.4 (SAS Institute, Inc. Cary, NC).

Determination of Sample Size

The determination of sample size was derived from clinical experience, in which we expected the clinical cure rates at day 5 to be approximately 20% and 80 % in the placebo and SCH-1 groups respectively. A sample of 15 patients per group will yield 87% power to detect a difference between 20% and 80%, based on a Fisher's exact test with a 0.05 significance level.

Changes in the Conduct of the Study or Planned Analyses

There were no changes in the conduct of the study or planned analysis.

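### No planned outcome tabulates, by arm, eyes whose injection or discharge grade rises above baseline, although worsening of viral infection is the harm the protocol itself names

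*Combined protocol and SAP*

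**What the plan says.** Section 2.1 says existing antibiotic/anti-inflammatory combinations are "contraindicated in the case of suspected viral infection due to their propensity to worsen the duration and severity of viral infections". Section 2.4 adds that "no current combination antibiotic/steroid combinations can safely be administered in suspected viral infections". Section 2.3 states that SCH1 contains a steroid, and the Synopsis indication includes viral disease.

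The outcomes planned against that background are:

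- **Primary endpoint (Section 4.1):** zero on both signs, or "clinical success defined as an overall decrease by 3 in the sum of both scores".
- **SAP test (Statistical and Analytic Plans):** a comparison of cure only, meaning zero on both signs.
- **Named safety outcomes (Synopsis, Assessment of Safety):** SPK at Day 1, "Incidence of SPK at Day 5 Intraocular pressure at Day 5", and acuity loss of at least four lines.
- **Rescue triggers (Section 6.4):** corneal infiltrate, intraocular inflammation and glaucoma.
- **Adverse events (Sections 10.6.1 and 10.6.4):** a broad definition, with questioning at every visit. Section 10.0 promises listings, and tables where suitable, but defines the safety population as recipients of SCH1.
- **Withdrawals (Section 6.3):** the investigator may withdraw a subject over safety or efficacy, and the reason goes on the CRF.

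Section 7.2 has both signs graded at Visits 1, 2 and 3.

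**The concern.** The protocol's case for SCH1 over existing products is that it can be given when a virus is suspected. Its own stated reason for caution is that steroid combinations can make viral disease worse. The reader of the final report will therefore want to know how many eyes got worse in each arm, and no planned analysis of the two graded signs answers that.

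Both efficacy definitions are binary. An eye going from 1/1 to 3/3 and an eye staying at 1/1 are both simply non-successes. The comparison of means planned in the Synopsis does not separate them either, because a few worsened eyes are averaged with a cured majority. The trial could meet its efficacy criterion and report every listed safety outcome without a count of worsened eyes.

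**Working it through.** **Inputs.** From the SAP: 15 per group, "clinical cure rates at day 5 to be approximately 20% and 80 % in the placebo and SCH-1 groups respectively", and power "based on a Fisher's exact test with a 0.05 significance level" stated as 87%. Also from the SAP: "All P-Values will be two-sided with statistical significance evaluated at the 0.05 alpha level". Both signs are graded 0 to 3 (Sections 9.1 and 9.2). The documents give no rate of worsening, so every such rate below is an assumption.

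**1. The plan's own figure.** Sum the binomial probabilities (n=15 per arm, rates 0.20 and 0.80) over all 16 × 16 outcome tables with two-sided Fisher p ≤ 0.05. Power is 87.2%, so the stated 87% reproduces.

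**2. How many non-successes a positive result leaves.** Take 3/15 vehicle successes, the assumed 20%. For 10/15 on SCH1:

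p = 2 × [C(15,10)C(15,3) + C(15,11)C(15,2) + C(15,12)C(15,1) + C(15,13)C(15,0)] / C(30,13)
= 2 × 1,516,620 / 119,759,850 = 0.025.

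With 9/15 the p-value is 0.060, so 10 is the minimum. That leaves 15 − 10 = 5 SCH1 eyes (33%) whose direction of change is not reported. At the planned 12/15 v 3/15 (p=0.0028) it leaves 3 (20%).

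**3. Worsened eyes at Day 5 sit only among the non-successes.** A cured eye has no sign raised. For an eye to succeed through a fall of 3 in the sum while one sign rises by 1, the other sign would have to fall by 4, which a 0 to 3 scale does not allow. So 5 is a true ceiling at Day 5 for this scenario. A rise at Visit 2 that resolves by Day 5 would come on top of it.

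**4. Means can hide the pattern (constructed example).** Every eye starts with a sum of 4. On SCH1, 12 are cured and 3 rise to 6. On vehicle, 3 are cured and 12 fall to 3.

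| | SCH1 | Vehicle |
|---|---|---|
| Cured | 12/15 (80%) | 3/15 (20%) |
| Mean Day 5 sum | (3×6)/15 = 1.2 | (12×3)/15 = 2.4 |
| Worsened | 3/15 (20%; exact 95% CI 4.3% to 48.1%) | 0/15 (0% to 21.8%) |

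The cure comparison (p=0.0028) and the mean both favour SCH1. The rank test also favours it (Mann-Whitney p=0.024); the t-test has the same direction but p=0.11. None of the four shows the three eyes at the top of the scale.

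**5. What a worsening table could and could not show.** The chance of at least one worsened eye among 15 is 1 − (1 − r)^15, which is 79%, 96% and 99.5% for r = 10%, 20% and 30%. A comparison of arms is much weaker. With none worsened on vehicle:

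- 3 v 0: p = 2 × C(15,3)/C(30,3) = 2 × 455/4,060 = 0.22
- 4 v 0: p = 2 × 1,365/27,405 = 0.10
- 5 v 0: p = 2 × 3,003/142,506 = 0.042

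Five or more are needed for significance. The power against a true 0% on vehicle is therefore P(X ≥ 5) = 1%, 16% and 48% at the same three rates.

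**The case against.** The strongest reply is that the plan does have routes by which deterioration would surface.

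- **SPK and acuity loss.** Both count some ways an eye gets worse. A reader might infer from this point that nothing planned counts deterioration of any kind. The documents do not support that; the gap concerns the two conjunctival grades.
- **Adverse events.** The definition does not exclude the treated disease, and all events are to be documented. So it cannot be said that worsening would never be tabulated. What stands is that no visible rule makes a rising grade an adverse event, so its appearance depends on reporting. The text between Sections 10.6.5 and 11.0 was not available to me, and a rule there cannot be excluded.
- **Withdrawals, symptom log and microbiological cure.** Withdrawal reasons are recorded, but no count by arm is planned. The daily symptom score has no definition of worsening. The Day 5 microbiological cure rate in the Synopsis bears on persistence of infection, although Section 7.2 lists no Visit 3 swab.

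The second objection is that the proposed table proves little: 15 per arm, mixed viral and bacterial disease, and follow-up that ends with treatment on Day 5 (Section 5.3). This is right, and it limits the table to description. It does not justify leaving the count out.

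The third is that a by-arm safety table has no vehicle group under the Section 10.0 population. The Synopsis promise of intention-to-treat analysis for everyone might be read as covering it, but Section 10.0 defines its own set. This objection also stands, and the fix has to deal with it.

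**Conclusion.** The point holds in a limited form. No planned outcome tabulates, by arm, eyes whose injection or discharge grade rises above baseline, although the protocol names that kind of harm as the reason for caution. In the scenario of 3/15 vehicle successes, a significant efficacy result is compatible with anything from 0 to 5 of 15 SCH1 eyes being worse at Day 5.

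That range is a ceiling, not an estimate. A reader might infer that SCH1 is expected to worsen infection, or that the worked example is likely; the documents give no rate and support neither. Nor should a clean table be read as evidence of safety in viral disease: 0/15 still has an exact upper limit of 21.8%, and prolongation after Day 5 is not observed.

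This is an inexpensive improvement that should be made. It is not a flaw in the efficacy test, whose stated power is correct on its own assumptions.

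**What to change.** Add to the Synopsis (Assessment of Safety) and to the SAP:

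- **Table.** For the study eye, the number and percentage in each arm improved, unchanged and worsened. Worsened means any increase over the Visit 1 grade in injection, discharge or their sum, at Visit 2, Visit 3 or the assessment at rescue or withdrawal, and takes precedence over improvement in the other sign. Give exact 95% confidence intervals for the worsened proportion in each arm and for the difference.
- **Listing.** Each worsened eye, with its grades by visit and its screening swab result.
- **Denominators.** The number of eyes at 3/3 at baseline, which cannot worsen on this scale, and the number with no post-baseline grade.
- **Population.** Restate the Section 10.0 safety population as all subjects who received at least one dose of SCH1 or placebo.
- **Limits.** State that the table is descriptive at 15 per arm and covers severity during treatment, not later prolongation of infection.

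Parts of the SAP are in the past tense. If the analysis has already been run, label the table as added afterwards.

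The cost is a paragraph, a table, a short listing and one corrected definition. No visit or procedure is added. The downside is that some one-grade rises will be grading noise; the vehicle arm shows how much.

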5.0 Trial Design

This is a Phase II single-center, double-masked, placebo controlled, randomized study of SCH1 for the treatment of infectious conjunctivitis. Approximately 30 subjects will be enrolled, who will be randomized in a 1:1 ratio between SCH1 and placebo. Subjects will be assessed at day 1, day 3, and day 5 for efficacy and safety.

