7.2 Study Procedures/Assessments

The second visit has a +/- 1 day window. The third visit has a +/-1 day window.

Visit 1

Perform the following activities on Visit 1 (baseline)

- Review

- BCVA

- SLE and tonometry

- DFE

- Grading of injection / discharge

- Dispense study medication

Visit 2

Perform the following activities on Visit 2

- Record AEs

- Review of current medications

- Visual acuity

- SLE

- Grading of injection / discharge

Visit 3

Perform the following activities on Visit 3

- Record AEs

- Review of current medications

- Visual acuity

SLE
Grading of injection / discharge
DFE

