8.2 Study Drug Administration

The study drug is administered as one drop to the affected eye every two hours while awake on Day 1, four times per day while awake for Day 2 through Day 5. The drugs are administered by the patient.

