10.2 Corneal Epithelium Grading

Corneal epithelium grading, including the presence of SPK, will be recorded at each visit.

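### The named SPK outcome uses Day 1 and Day 5 only, so corneal SPK that appears by Day 3 and clears by Day 5 is left out of it, although Day 3 SPK is recorded

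*Combined protocol and SAP*

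**What the plan says.** The synopsis, in its Assessment of Safety row, lists "Incidence of SPK at day 1" and "Incidence of SPK at Day 5" among four safety items. The other two are intraocular pressure at Day 5 and a visual acuity loss criterion.

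Data collection is wider than that. Section 10.2 states: "Corneal epithelium grading, including the presence of SPK, will be recorded at each visit". Section 5.0 sets the visits: "Subjects will be assessed at day 1, day 3, and day 5 for efficacy and safety". In the Schedule of Visits and Assessments, the row "Anterior segment slit lamp exam and tonometry" is marked at all three visits, and Section 7.2 lists a slit-lamp examination at Visit 2.

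On timing, Section 7.2 puts "Dispense study medication" last among the Visit 1 activities. Section 8.2 gives one drop "every two hours while awake on Day 1" and then four drops a day through Day 5. Section 7.2 also says: "The second visit has a +/- 1 day window", and it allows Visit 3 the same tolerance.

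No section defines SPK incidence at Day 3, at any post-dose visit, or as a worst grade. The SAP covers clinical cure and general descriptive statistics and does not mention SPK.

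**The concern.** A corneal surface effect of the drops could be greatest soon after the most frequent dosing and fade as the frequency falls. Visit 2 is the examination best placed to see that pattern, and it is the one reading absent from the named outcome. An early, transient effect would then be understated in the SPK figures that the synopsis singles out, even though the observations exist.

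This differs from the question of how to treat SPK already present at entry. A sound baseline rule applied to Day 5 alone would still miss SPK that came and went between visits.

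The synopsis also calls for a safety summary to the IRB every three months and at study end. If that summary follows the items listed in the synopsis, the gap reaches safety monitoring as well as the final report.

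**Working it through.** **Comparison of time points**

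| | Day 1 (Visit 1) | Day 3 (Visit 2) | Day 5 (Visit 3) |
|---|---|---|---|
| SPK recorded (Section 10.2) | yes | yes | yes |
| Slit-lamp examination (schedule; Section 7.2) | yes | yes | yes |
| In the named SPK outcome (synopsis) | yes | **no** | yes |
| Position relative to dosing (Sections 7.2, 8.2) | apparently pre-dose | after the two-hourly day | after the four-times-daily days |

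The windows put Visit 2 at 3 ± 1, or Day 2 to 4, and Visit 3 at 5 ± 1, or Day 4 to 6. That Day 1 is pre-dose is an inference from the order of the Visit 1 list. The documents do not state it outright.

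**Plan's own figure.** There is none for SPK. The SAP's one complete power statement concerns clinical cure: 15 per group, 20% against 80%, Fisher's exact test, two-sided 0.05, 87%. Full enumeration of the two binomials gives 87.2%, so it reproduces, but it has no bearing on SPK.

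**Illustration on assumed values.** Let n = 15 (SCH1 subjects, from the synopsis), q = the share with SPK on Day 3 that was not there on Day 1, and h = the share of those who are clear by Day 5. Both q and h are assumptions. Treating subjects as independent:

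- expected number omitted from the named outcome = n × q × h
- chance that at least one is omitted = 1 − (1 − qh)^n

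With h = 50%:

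- q = 10%: 15 × 0.10 × 0.50 = 0.75 subjects; 1 − 0.95^15 = 54%
- q = 20%: 15 × 0.20 × 0.50 = 1.5 subjects; 1 − 0.90^15 = 79%
- q = 40%: 15 × 0.40 × 0.50 = 3.0 subjects; 1 − 0.80^15 = 96%

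With h varied from 25% to 100% and q from 10% to 40%, the expected number runs from 15 × 0.10 × 0.25 = 0.4 to 15 × 0.40 × 1 = 6. The chance of omitting at least one runs from 32% to above 99%. With h = 0 (all SPK persists to Day 5) nothing is omitted.

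**The case against.** **Day 3 findings have other outlets.** Section 10.0 promises subject listings, and summary tables where they are thought suitable. Section 10.6.1 defines an adverse event broadly, without requiring a causal link. Section 10.6.4 has events that the investigator observes documented, and the schedule marks adverse event assessment on Day 3. This stands. A reader might infer that Day 3 SPK is discarded or never counted, and the documents do not support that. What remains is that neither outlet is a defined SPK comparison: no section requires a Day 3 SPK table or requires SPK to be entered as an event.

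**There is no SPK test to lose power.** A reader might put the loss in terms of power. For example, at 50% against 10% with 15 per arm, two-sided Fisher power is 54% for any post-dose visit and 17% for Day 5 alone if half has healed (25% against 5%). The arithmetic is right, but the rates are invented and the SAP names tests for clinical cure only. With the same healing, 30% against 10% goes from 15% to 3%, and 20% against 10% from 4% to 0.6%, so neither definition would serve as a test at such rates. These figures are not a cost to this plan.

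**The bias is conditional.** Dosing continues through Day 5. If SPK accumulates or persists under it, the Day 5 reading captures it. This stands: the documents do not say which pattern to expect.

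**Visit 2 is not tightly tied to peak exposure.** A Visit 2 on Day 4 comes well after the two-hourly dosing and may nearly coincide with Visit 3. This also stands. Visit 2 is the first scheduled look after Day 1, but not necessarily a close one.

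**Fixed-visit incidence is a legitimate choice** in a 30-subject phase II trial with an efficacy objective. That is fair, and it limits the weight of the point. It does not explain leaving a scheduled reading out of the outcome when using it costs almost nothing.

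**Conclusion.** The point holds in a limited form. As defined in the synopsis, the SPK outcome has one post-dose reading, Day 5, and omits SPK that arises by Day 3 and clears by Day 5. If SPK is early and transient, the named outcome understates it; if it persists, little is lost. On assumed rates of 10% to 40% on Day 3 with half healed, the average omission is 0.75 to 3 of 15 treated subjects. That range rests wholly on the assumptions, because the documents give no SPK rate.

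The conclusion depends on the Day 1 reading being taken before the first drop, as the Visit 1 list suggests. It does not affect the primary endpoint, the sample size or any planned test. It is an inexpensive improvement to the safety reporting and does not invalidate it.

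**What to change.** In the synopsis and the SAP, define the SPK outcome as new or worsened SPK relative to the Day 1 reading at any post-dose visit (Day 3 or Day 5), in the study eye, reported for each arm. Tabulate the worst post-dose grade descriptively, with no test. Keep Day 5 incidence as the measure of persistent SPK and Day 1 as the baseline, and state that the Day 1 reading precedes the first drop. The baseline comparison is needed: without it, SPK present at entry would count in both arms and blur the contrast.

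The cost is one definition and one table from slit-lamp data already scheduled. There is no new visit or procedure and no change to treatment. The reported SPK rate may be slightly less favourable.

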2.3 SCH1

SCH1 is a novel combination anti-infective / steroid eye drop with *in vitro* efficacy against many bacteria, yeasts, fungi and human adenovirus. The product contains two FDA-approved active pharmaceutical ingredients (Pred Forte, or prednisolone acetate 1%, application #017011, approved May 30, 1973; chlorhexidine gluconate, approved December 28, 1995). The combination is formulated as a 0.2% chlorhexidine 1% prednisolone acetate ophthalmic suspension. In preclinical evaluation, it demonstrated antimicrobial efficacy on contact with ocular isolates of *S.aureus*, *P. aeruginosa*, *E. coli*, *C. albicans*, and *A. brasiliensis*. A review of preclinical studies is provided in the investigators brochure.

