10.0 Assessment of Safety

The safety population is defined as all subjects who received one or more doses of SCH1. Standard summary and/or analysis techniques will be used for the evaluation of AEs, vital sign measurements, clinical laboratory results and physical examinations, and these are to be detailed within the body of the report. The safety data will be presented in individual listings and summary tables where appropriate.

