10.3 Intraocular Pressure

Intraocular pressure will be measured by tonometry at screening and at each visit.

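### Section 10.0 defines the safety population by receipt of SCH1 alone, so read literally every safety summary, including intraocular pressure, loses its placebo comparator

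*Combined protocol and SAP*

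**What the plan says.** **The product.** Section 2.3: "The combination is formulated as a 0.2% chlorhexidine 1% prednisolone acetate ophthalmic suspension". The protocol treats pressure as a steroid risk: Section 6.2 excludes known steroid responders, and Section 6.4 makes onset of glaucoma a reason for rescue.

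**Who is in the safety analysis.** Section 10.0: "The safety population is defined as all subjects who received one or more doses of SCH1". The SAP gives no other definition. The Statistical Analysis row of the synopsis, by contrast, applies an intent-to-treat "analysis for all patients. Mean outcome variables in the two study groups will be compared".

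**When pressure is measured.** Section 10.3: "Intraocular pressure will be measured by tonometry at screening and at each visit". The Schedule of Visits marks "Anterior segment slit lamp exam and tonometry" on Days 1, 3 and 5. Section 7.2 names tonometry at Visit 1 but lists only the slit lamp examination at Visits 2 and 3.

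**How pressure is analysed.** The Assessment of Safety row of the synopsis gives "Intraocular pressure at Day 5". The remaining text is general. Group means "will be analyzed by both parametric and non-parametric tests to allow for deviations of data from normal distributions" (synopsis), and SAP descriptive statistics "were calculated for all relevant measures". Nothing says whether the screening reading enters the Day 5 comparison.

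**The concern.** A safety population needs the control arm, because SPK, visual acuity loss, adverse events and pressure changes can all arise from the conjunctivitis itself or from the vehicle. Without placebo patients in the set, a raised pressure or an SPK rate on SCH1 cannot be set against what happened without the active ingredients. The Section 10.0 wording governs all safety data; pressure is the clearest example because the steroid is the reason for measuring it.

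A smaller matter concerns the same data. A screening pressure is taken from every patient, but the plan gives it no role in the Day 5 comparison. With 15 patients per arm, any precision that reading offers is worth having, since it costs nothing to collect.

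**Working it through.** **1. The population, by comparing sections.**
- Section 5.1 randomises patients 1:1 to either SCH1 or placebo.
- Section 6.4 refers to stopping dosing with SCH1/placebo, naming both.
- Section 8.0 identifies SCH1 as the study drug and placebo as vehicle only.
- Section 10.0 names SCH1 only.

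Since the protocol writes both names when it means both arms, SCH1 alone in Section 10.0 does not naturally cover placebo. If all 30 patients are dosed, the literal safety set is 15 SCH1 patients and 0 placebo patients. The corrected set is 15 and 15.

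**2. Plan figures.** Neither document states a figure for pressure. The SAP's only power figure, 87% for clinical cure with 15 per arm, reproduces as 87.2% by exact enumeration of the two-sided Fisher test. It has no bearing on safety.

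**3. Precision of the Day 5 pressure difference.** Inputs: 15 per arm (synopsis, SAP) and two-sided 0.05 (SAP). The pressure SD and the correlation ρ between screening and Day 5 are not in the documents; both are assumed and shown over a range.

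- Unadjusted 95% half-width = t(28) × SD × √(2/15), with t(28) = 2.0484 and √(2/15) = 0.3651.
- Adjusted half-width = t(27) × SD × √(1 − ρ²) × √(2/15) × √(1 + 1/26), with t(27) = 2.0518. The last factor, 1.0190, allows for estimating the slope.

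For SD 3 mmHg and ρ = 0.5:
- unadjusted: 2.0484 × 3 × 0.3651 = 2.24 mmHg
- adjusted: 2.0518 × 3 × 0.8660 × 0.3651 × 1.0190 = 1.98 mmHg

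| SD (mmHg) | Unadjusted | ρ = 0.3 | ρ = 0.5 | ρ = 0.7 |
|---|---|---|---|---|
| 2.5 | 1.87 | 1.82 | 1.65 | 1.36 |
| 3 | 2.24 | 2.18 | 1.98 | 1.64 |
| 4 | 2.99 | 2.91 | 2.64 | 2.18 |
| Narrowing | – | 2.6% | 11.6% | 27.1% |

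The SD cancels from the ratio, which is (2.0518/2.0484) × 1.0190 × √(1 − ρ²) ≈ 1.021 × √(1 − ρ²). At ρ = 0.2 this is 1.000, so there is no gain. At ρ = 0.1 it is 1.016, a loss of 1.6%.

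**4. What adjustment does not do.** In a simulation of 20,000 trials per setting (SD 3, ρ from 0.3 to 0.8), one of 15 SCH1 patients was given a 10 mmHg rise. The t-test rejected in 4.6% to 5.0% of trials and the adjusted model in 3.6% to 4.8%. With two such patients the figures were 8.7% to 9.0% and 8.7% to 9.2%. The model therefore finds isolated rises no better than the plain comparison. Nor is a count a test: Fisher's p against 0/15 is 0.48 at 2/15 and first falls below 0.05 at 5/15 (0.042). Observing 0 of 15 still allows a true rate of up to 21.8% (two-sided exact 95% limit).

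**The case against.** **On the population.** The sentence is probably a slip: placebo patients are examined on the same schedule, their adverse events are recorded, and the synopsis statement on all patients points to both arms. The likelihood of a slip is fair, but two conflicting statements remain, and the specific definition is the wrong one.

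**On adjustment.** The existing comparison is unbiased under randomisation, the gain depends on an unknown correlation, and exposure is five days in a trial whose stated objective is efficacy. All of that stands. Adjustment is an improvement, not the repair of an error.

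**Stronger readings that the documents do not support.** A reader might infer the following.
- *Individual pressure rises would surface only in listings or adverse event reports.* Section 10.0 also provides summary tables where appropriate. The synopsis provides review by the Medical Monitor and sponsor, with a safety summary to the IRB every three months and at study end.
- *A patient rescued for glaucoma has no required pressure reading.* Section 6.4 calls for the Visit 3 evaluations, and the schedule and Section 10.3 require tonometry at that visit. The Section 7.2 list is plainly abbreviated: at Visit 3 it also omits vital signs and the comfort exam, which the schedule marks.
- *The study-eye rule in Section 4.3 is deficient because it covers only the primary analysis.* Leaving safety open to every treated eye is reasonable.
- *A fixed threshold such as 10 mmHg is missing and needed.* Its choice is debatable. With symmetric measurement noise, a true 10 mmHg rise at one visit reaches the cut about half the time. If the rise is present at both later visits, the chance is 1 − (1/4 + arcsin(0.5)/2π) = 67%, assuming equal correlation among the three readings.

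**Conclusion.** The safety population is wrong as written and should be corrected. Followed literally, it removes the comparator from all safety summaries, 15 against 0 instead of 15 against 15 if all 30 patients are dosed. This conclusion rests on the text alone and needs no assumption about pressure.

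Using the screening pressure is a secondary recommendation. Its benefit runs from none (correlation 0.2 or below) through about 3% and 12% to 27% (0.3, 0.5 and 0.7), on assumed values. The Section 7.2 discrepancy is a matter of wording. The practical weight is modest: treatment lasts five days, known responders are excluded, and 30 patients cannot settle safety under any analysis.

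**What to change.** 1. **Section 10.0, repeated in the SAP:** *Safety population: every subject given at least one dose of either SCH1 or placebo, analysed by treatment received.* Cost: one sentence.
2. **Synopsis safety row, Section 10.3 and SAP (secondary):** report the between-arm difference in study-eye pressure at Day 5, or at End of Treatment for patients who are rescued or withdraw, with a 95% confidence interval from a linear model containing treatment and the screening pressure of the same eye. Cost: one degree of freedom and a few lines of analysis; if the correlation proves very low, the interval widens slightly.
3. **Section 7.2:** add tonometry at Visits 2 and 3, to agree with the schedule and Section 10.3.
4. **Optional:** a descriptive per-arm count of pressure rises from screening, with denominators, labelled as a display rather than a test. The sponsor should choose the cut in advance.

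No patient, visit or measurement is added, since the protocol already requires tonometry at all three visits.
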